8.6.3 Primary Efficacy Endpoint

The primary efficacy endpoint is the reduction from baseline to week 8 in frequency of seizures (normalized to a 4-week rate): observable seizures measured for 6 weeks after 2-week titration by diary and absence seizures measured overnight by electroencephalography (EEG). Observable seizure frequency at baseline will be calculated based on approximately 6 weeks between the screening and randomization visits and observable seizure frequency at week 8 will be calculated based on approximately 6 weeks between the end of titration and the week 8 visit (see Section 5.7.1). Absence seizure frequency will be based on overnight EEG at the randomization and week 8 visits.

The primary efficacy endpoint will be derived for each subject based on subject seizure type at randomization: observable seizures from the diary will be used for Observable Seizures Subjects and absence seizures from EEG will be used for Absence Seizures Only Subjects (see Section 5.6).

The primary efficacy endpoint will be analyzed, based on the Efficacy Analysis Set, using a linear regression (ANCOVA) model as described for continuous endpoints in Section 8.6.1. Logarithmic transformations will be used for modeling. The response variable in the model will be the reduction in the natural logarithm of the seizure frequency (+ 1) from baseline to Week 8 and the baseline covariate will be the natural logarithm of the baseline seizure frequency (+ 1): observable seizures from the diary will be used for Observable Seizures Subjects and absence seizures from EEG will be used for Absence Seizures Only Subjects.

An additional covariate will be included that indicates whether the subject is an Observable Seizures Subject or an Absence Seizures Only Subject. Estimates and 90% confidence intervals of percent reduction in seizure frequency will be derived from the model for each treatment group and for the difference between groups.

Missing data will be imputed as specified in Section 7.1. Sensitivity analysis assessing the impact of missing data will be performed using the methods described in Section 7.1.

Percent reduction from baseline in frequency of seizures over the entire study period will be summarized by visit (see Section 5.7.1), and by treatment group, for subjects while taking UX007, and overall.

The following additional analyses will be performed:

- An analysis will be performed incorporating multiplicity adjustment for analyses of absence and observable seizures using a fallback method (Wiens et al. 2005). The absence seizures and observable seizures analyses may include overlapping subjects. For each of these subgroups, a within UX007 group test will be performed first and the between group test will only be performed if the p-value for the within group test is less than the appropriate level according to the procedure. The one-sided type I error ($\alpha=0.05$) will be split into 3 components: $\alpha_1(\text{Overall}) = 0.04$, $\alpha_2(\text{Absence}) = 0.005$, $\alpha_3(\text{Observable}) = 0.005$. The following null hypotheses will be tested:
 - $H_{01}(\text{Overall, Between Group})$: Reduction from baseline to week 8 in frequency of seizures with UX007 is not greater than with placebo
 - $H_{02W}(\text{Absence, Within Group})$: Reduction from baseline to week 8 in frequency of *absence* seizures with UX007 is not greater than zero
 - $H_{02B}(\text{Absence, Between Group})$: Reduction from baseline to week 8 in frequency of *absence* seizures with UX007 is not greater than with placebo
 - $H_{03W}(\text{Observable, Within Group})$: Reduction from baseline to week 8 in frequency of *observable* seizures with UX007 is not greater than zero
 - $H_{03B}(\text{Observable, Between Group})$: Reduction from baseline to week 8 in frequency of *observable* seizures with UX007 is not greater than with placebo

The corresponding nominal p-values are defined as $p_1(\text{Overall})$, $p_{2W}(\text{Absence})$, $p_{2B}(\text{Absence})$, $p_{3W}(\text{Observable})$, $p_{3B}(\text{Observable})$. The testing procedure will be performed as follows:

1. If $p_1 \leq \alpha_1 = 0.04$, then reject H_{01} and set $\alpha_2^* = \alpha_1 + 0.005$; otherwise, accept H_{01} and set $\alpha_2^* = 0.005$.
2. If $p_{2W} \leq \alpha_2^*$, then reject H_{02W} ; otherwise, accept H_{02W} , accept H_{02B} and set $\alpha_3^* = 0.005$.
3. If $p_{2W} \leq \alpha_2^*$ and $p_{2B} \leq \alpha_2^*$, then reject H_{02B} and set $\alpha_3^* = \alpha_2 + 0.005$; otherwise, accept H_{02B} and set $\alpha_3^* = 0.005$.

4. If $p_{3W} \leq \alpha_3^*$, then reject H_{03W} ; otherwise, accept H_{03W} and accept H_{03B} .
 5. If $p_{3W} \leq \alpha_3^*$ and $p_{3B} \leq \alpha_3^*$, then reject H_{03B} ; otherwise, accept H_{02B} .
- An analysis will be performed with seizure frequency at baseline and Week 8 derived for each subject based on subject seizure type at randomization: observable seizures from the diary will be used for Observable Seizures Only Subjects and absence seizures from EEG will be used for Absence Seizures Subjects (see Section 5.6).
 - An analysis will be performed using observable seizure frequency at week 8, including titration period, calculated based on seizure diary data collected for approximately 8 weeks from baseline to week 8.
 - An analysis will be performed using the Per Protocol Analysis Set.
 - An analysis will be performed using the alternative imputation methods described in Section 7.1.

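### In the supplementary fallback analysis, a UX007-only before-after test gates each seizure type's randomised comparison; the gate adds no error control, and passing it is not evidence of a drug effect.

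*SAP*

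**What the plan says.** After the primary ANCOVA, SAP 8.6.3 lists several additional analyses. The first is a fallback procedure covering the overall, absence and observable seizure results. One-sided alpha of 0.05 is split into 0.04 (overall), 0.005 (absence) and 0.005 (observable).

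The overall hypothesis H01 compares UX007 with placebo and has no gate. Each seizure type has two hypotheses:

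- A within-group null with no placebo term. For absence (H02W), the reduction in "frequency of *absence* seizures with UX007 is not greater than zero". H03W says the same for observable seizures.
- A between-group null. For absence (H02B), the reduction in "frequency of *absence* seizures with UX007 is not greater than with placebo". H03B is the observable counterpart.

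The order is fixed: "a within UX007 group test will be performed first and the between group test will only be performed if" the within-group p-value meets the current level. If it does not, H02B (step 2) or H03B (step 4) is accepted untested. If it does, H02W or H03W is formally rejected, whatever the between-group test then shows.

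Two other places set the context. SAP 8.6.4 plans between-group ANCOVAs for observable and for absence seizures as secondary analyses, with no gate. Protocol 7.6 states that secondary and exploratory analyses get no multiplicity adjustment.

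**The concern.** This procedure is the plan's only alpha-controlled route to a statement about absence or observable seizures separately. Inside it, a single-arm change can receive a formal rejection, and a randomised comparison can go untested because of that single-arm result.

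A fall from baseline on UX007 mixes any drug effect with placebo response, time trend and regression to the mean. Regression is plausible here. Protocol 7.3.1 requires a minimum recent seizure count, or absence seizures on the Screening EEG. SAP 5.6 then assigns seizure type partly on the baseline frequency from which change is measured: an observable frequency of at least 4, or an EEG absence frequency above 0. Only the placebo arm can separate these components.

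Two things are at stake: a within-group rejection being read as a seizure-type effect of UX007, and a real between-arm difference being lost because the UX007 arm alone did not move enough.

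**Working it through.** **Inputs from the documents.** Alpha split and steps: SAP 8.6.3. About 40 completers, a 50-point difference, SD 55 points, two-sample t test, one-sided 0.05: SAP 3.5. Allocation 3:1, so about 30 and 10: SAP 3.3.

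**Assumptions not in the documents.** Overlapping subgroups of 20 UX007 and 7 placebo subjects; the overall SD of 55 applied to each subgroup; correlation 0.3 between seizure types within a subject; percent reductions normally distributed; the within-group test taken as a one-sample t test. The SAP itself models log(frequency + 1) by ANCOVA, so the figures are indicative.

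**1. The plan's own figures.** 0.04 + 0.005 + 0.005 = 0.05, as stated. For power, the noncentrality is 50 / (55 × √(1/30 + 1/10)) = 50 / 20.08 = 2.49 on 38 degrees of freedom. This gives 0.788 with the noncentral t and 0.801 with the normal approximation, so about 80% is reproduced.

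**2. Levels as printed.** `α2*` is 0.04 + 0.005 = 0.045 if H01 is rejected, otherwise 0.005. Step 3 passes on `α2` (0.005), so `α3*` is at most 0.005 + 0.005 = 0.010.

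**3. One within-group test, no drug effect, both arms falling by 20 points.** Noncentrality is 20 / (55/√n).

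| UX007 n | Noncentrality | P(reject) at 0.045 | P(reject) at 0.005 |
|---|---|---|---|
| 30 | 20 / 10.04 = 1.99 | 0.60 | 0.24 |
| 15 | 20 / 14.20 = 1.41 | 0.36 | 0.09 |

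The between-group test stays at its nominal level, 0.045 or 0.005.

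**4. All five steps simulated, no drug effect.**

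| Shared fall (points) | At least one of H02W, H03W rejected |
|---|---|
| 0 | about 1.4-1.7% |
| 10 | about 7-8% |
| 15 | about 14-15% |
| 20 | about 24-27% |

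The chance of any between-arm rejection stays at 4-5%.

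**5. Is the gate needed for error control?** The fallback split alone controls the family H01, H02B, H03B at 0.05. With the gate removed, the simulated between-arm family error is 4.2-4.8%.

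**6. Can the gate add a between-arm rejection?** No. With the gate, H02B needs both p2W and p2B at or below `α2*`; without it, only p2B. So every gated rejection of H02B also occurs ungated. `α3*` is raised only when H02B is rejected, so it is never lower without the gate, and the same holds for H03B.

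**7. Power with and without the gate, true difference 50 points.**

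| UX007 change | Placebo change | Hypothesis | Gated | Ungated |
|---|---|---|---|---|
| falls 50 | flat | H02B | 55.5% | 55.7% |
| falls 30 | rises 20 | H02B | 47% | 55% |
| falls 30 | rises 20 | H03B | 22% | 32% |

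The losses in the second scenario are 55 − 47 = 8 and 32 − 22 = 10 points.

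**The case against.** The strongest case is that little harm follows. The procedure is one additional analysis, and the within-group hypotheses are plainly labelled as such. Nothing in SAP 8.6.3 says that rejecting H02W or H03W supports an efficacy claim. A within-group rejection alone passes no alpha forward, since step 3 raises `α3*` only if the between-group test also succeeds. Requiring UX007 both to improve on its own baseline and to beat placebo is a stricter criterion that a sponsor may choose. All of this stands and limits the weight of the point.

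Three stronger readings are tempting, and the documents do not support them.

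- A reader might set the 7-27% rejection rates against a nominal 5% and call it inflated error. With a shared fall, the within-group nulls are false, so rejecting them is correct. When neither arm changes, the rate is about 1.4-1.7%.
- A reader might infer that the placebo comparison by seizure type could be missing from the trial. SAP 8.6.4 and Table 6 plan both ANCOVAs unconditionally. The comparison can be skipped only inside the fallback procedure.
- A reader might compare the high power of the within-group test with the lower power of the between-group test and call the gap a cost of the gate. That only contrasts a one-sample test with a 3:1 two-sample test.

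The power loss also depends on placebo worsening, which the documents give no reason to expect.

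What remains is that the gate does no statistical work for the randomised hypotheses, and that the ungated secondary comparisons carry no multiplicity adjustment.

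**Conclusion.** The point holds as a minor one. Within the fallback procedure, H02W and H03W are valid tests of their own nulls but not of UX007 against placebo, and they can stop H02B and H03B from being tested. The gate buys no error control and can only remove rejections of the randomised hypotheses. Its power cost is negligible if placebo is flat and about 8-10 points in the worsening scenario examined. Under equal falls of 10 to 20 points in both arms, a within-group rejection occurs in roughly 7% to 27% of trials with no drug effect; this shows how often it could mislead if read as a drug effect. These sizes rest on the assumed 20/7 subgroups, SD of 55, correlation of 0.3 and normal percent reductions. The ordering result in step 6 of the working depends on none of these. The primary ANCOVA and the secondary seizure-type ANCOVAs are not affected.

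**What to change.** In SAP 8.6.3, delete H02W and H03W from the hypothesis list and from steps 2 to 5. Test H02B directly at `α2*` and H03B directly at `α3*`. Report the UX007 within-group change for each seizure type descriptively, with its 90% confidence interval, outside the procedure.

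The cost is SAP wording only. The alpha split stays as it is, and no new data are needed. The sponsor gives up a formal rejection based on single-arm change.

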## **7.6 Statistical Methods and Determination of Sample Size**

The completeness of the data affects the integrity and accuracy of the final study analysis. Therefore, every effort will be made to ensure complete, accurate and timely data collection, and to avoid missing data.

The procedures for handling missing, unused, or spurious data, along with the detailed method for analyses will be presented in the Statistical Analysis Plan (SAP); in general, missing data will be treated as missing. The information below is intended as a guide to planned analyses. Planned analyses will occur at the end of the double-blind Treatment Period, and at the end of the study (Extension Period).

The statistical analyses will be reported using summary tables, figures, and data listings. Statistical tests will be at one-sided alpha level of 0.05. All analyses and tabulations will be performed using SAS®. Continuous variables will be summarized with means, standard deviations, medians, minimums, and maximums. Categorical variables will be summarized by counts and by percentages of subjects in corresponding categories. All raw data obtained from the CRFs as well as any derived data will be included in data listings.

Each secondary endpoint will be tested independently. No adjustments for multiple comparisons on secondary and exploratory analyses will be performed. The statistical method employed for the analysis of each assessment will be defined in more detail in the SAP.

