3.5 Sample Size Considerations

The proposed Phase 2 study will have a sample size that would likely detect a 50% reduction from baseline in seizure frequency compared to placebo. Such a treatment effect would be greater than or equal to that demonstrated by many of the approved AEDs for refractory epilepsy, such as lamotrigine, oxcarbazepine and levetiracetam ([Glauser et al. 2000](#)), ([Glauser et al. 2006](#)), ([Trevathan et al. 2006](#)). A theoretical treatment effect of this magnitude, in light of the benign safety profile of UX007 shown to date, is considered to be clinically meaningful by physician experts. From the perspective of accurately determining seizure frequency, the proposed durations are deemed sufficient and are accounted for in the standard deviation (55%) used in the power calculation.

For the study to be adequately powered, a sample of approximately 40 completed subjects was estimated to be adequate to detect a 50% between-group difference in seizure frequency per 4 weeks with power of approximately 80% and population standard deviation of 55% using two-sample t test at one-sided alpha level of 0.05.

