8 STATISTICAL METHODS OF ANALYSIS

8.1 General Principles

During the Double-Blind Placebo-Controlled Treatment Period, efficacy analyses will be based on the Efficacy Analysis Set or the Per Protocol Analysis Set. During the open label period, efficacy analyses will be based on the Extension Set. Safety analyses will be based on the Safety Analysis Set. Unless stated otherwise, statistical tests will be 1-sided hypothesis tests performed at the 5% level of significance and confidence intervals will be 2-sided 90% confidence intervals. Continuous variables will be summarized by number of subjects and mean, standard deviation (SD), median, minimum, and maximum values. Categorical variables will be summarized by number and percentage of subjects.

Analyses and summaries by study period will be done for the following time periods:

- Double-blind placebo-controlled treatment period: after the date of the randomization visit until the date of the week 8 visit
- Open-label extension period: after the date of the week 8 visit until the date of the week 52 visit
- Dose exploration period: after the date of the week 26 visit until the date of the week 36 visit

Overall analyses and summaries will include all subjects and ignore treatment assignment.

For logarithmic transformations of seizure frequency, the natural logarithm will be used and a value of 1 will be added prior to performing the transformation.

For analyses and summaries of subjects while taking UX007, the time while taking placebo will be excluded and the original baseline will be used for all subjects regardless of which treatment was taken during the double-blind placebo-controlled treatment period.

Graphical displays of select study endpoints will be completed and include both observed study data and modeled analyses. Arithmetic means, least square means (LSM), and appropriate measure of dispersion (e.g., standard deviation, standard error) or confidence intervals may be displayed in figures.

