8.6.4 Secondary Endpoints

For secondary endpoints, between group comparisons from baseline to week 8 will be performed as described in Section 8.6.1 as follows:

- Seizure response at Week 8 (a percent reduction from baseline in seizure frequency greater than or equal to 50%, see Section 5.7.4) will be analyzed, based on the Efficacy Analysis Set, using logistic regression. The baseline covariate will be the natural logarithm of the baseline seizure frequency (+ 1): observable seizures from the diary will be used for Observable Seizures Subjects and absence seizures from EEG will be used for Absence Seizures Only Subjects. An additional covariate will be included that indicates whether the subject is an Observable Seizures Subject or an Absence Seizures Only Subject.
- Reduction from baseline in frequency of observable seizures will be analyzed, based on the Efficacy Analysis Set, using linear regression. The response variable in the model will be the change in the natural logarithm of the observable seizure frequency (+ 1) from baseline to Week 8 and the baseline covariate will be the natural logarithm of the baseline frequency (+ 1) of observable seizures (see Section 5.7.5). Estimates and 90% confidence intervals of percent reduction in observable seizure frequency will be derived from the model for each treatment group and for the difference between groups.
- Observable seizure response at Week 8 will be analyzed, based on the Efficacy Analysis Set, using logistic regression. Observable seizure frequency will be calculated based on approximately 6 weeks between the end of titration and the week 8 visit. The baseline covariate will be the natural logarithm of the baseline frequency (+ 1) of observable seizures (see Section 5.7.5).
- Reduction from baseline in frequency of absence seizures will be analyzed, based on the Efficacy Analysis Set, using linear regression. The response variable in the model will be

the change in the natural logarithm of the absence seizure frequency (+ 1) from baseline to Week 8 and the baseline covariate will be the natural logarithm of the baseline frequency (+ 1) of absence seizures. Estimates and 90% confidence intervals of percent reduction in absence seizure frequency will be derived from the model for each treatment group and for the difference between groups.

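### Step 3 of the supplementary fallback procedure passes on the wrong alpha, so observable seizures are tested at 0.010 instead of 0.050, and step 5 closes the wrong hypothesis

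*SAP*

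**What the plan says.** The procedure is in SAP 8.6.3, after the sentence "The following additional analyses will be performed". One-sided 0.05 is split into α₁ = 0.04 (overall), α₂ = 0.005 (absence) and α₃ = 0.005 (observable). For absence and for observable seizures, a within-UX007 test (W) must pass before the comparison with placebo (B). The instructions that matter are:

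- Step 1, if H01 is rejected at 0.04: "set $\alpha_2^* = \alpha_1 + 0.005".

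- Step 3, if both absence p-values are at or below α₂∗, so that H02B is rejected: "set $\alpha_3^* = \alpha_2 + 0.005".

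- Step 5, after comparing both observable p-values with α₃∗: "then reject H_{03B} ; otherwise, accept H_{02B".

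Two other places fix the scope. SAP 8.1 sets the default: "Unless stated otherwise, statistical tests will be 1-sided hypothesis tests performed at the 5% level of significance". Observable seizures also have their own secondary analysis in SAP 8.6.4 ("Reduction from baseline in frequency of observable seizures will be analyzed, based on the Efficacy Analysis Set, using linear regression"), and Protocol 7.6 leaves secondary tests unadjusted: "Each secondary endpoint will be tested independently. No adjustments for multiple comparisons on secondary and exploratory analyses will be performed".

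**The concern.** Step 3 tests the absence hypothesis at the starred level and then passes on the unstarred one. The 0.04 released by rejecting H01 reaches absence seizures and goes no further, so the last hypothesis can never receive more than 0.010 of the 0.05 set aside for the family.

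Step 5 has a separate defect. If the observable within-group test passes and the between-group test fails, H03B has no stated outcome. Instead H02B is accepted, although step 3 may already have rejected it. Read literally, the same clause also applies when the within-group test fails, so any failure to reject H03B would reverse an earlier rejection of H02B.

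This is the only multiplicity-adjusted route the SAP gives to separate statements on absence and observable seizures. A programmer must either code a wrong threshold and a contradictory rule or depart from the SAP. A correction made after unblinding, with an observable p-value between 0.010 and 0.050, would look data-driven.

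**Working it through.** **Inputs.** Alpha split and steps 1 to 5: SAP 8.6.3. Difference 50, SD 55, about 40 completed subjects, power about 80%, "using two-sample t test at one-sided alpha level of 0.05": SAP 3.5. Allocation 3:1: SAP 3.3. The size of the observable-seizure subset is not given; 24:8 and 21:7 are assumptions.

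**Plan's own figures.** The split adds up: 0.04 + 0.005 + 0.005 = 0.05. Power for 30:10 also reproduces. The standard error is 55 × √(1/30 + 1/10) = 20.08 and the noncentrality is 50/20.08 = 2.49. With 38 degrees of freedom the one-sided 5% critical value is 1.686, which gives power 0.788 (0.801 by the normal approximation), against about 80% stated.

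**Level for observable seizures on each path.**

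| H01 | H02B | α₂∗ | α₃∗ as written | α₃∗ with α₂∗ carried |
|---|---|---|---|---|
| rejected | rejected | 0.045 | 0.005 + 0.005 = 0.010 | 0.045 + 0.005 = 0.050 |
| rejected | not rejected | 0.045 | 0.005 | 0.005 |
| not rejected | rejected | 0.005 | 0.010 | 0.010 |
| not rejected | not rejected | 0.005 | 0.005 | 0.005 |

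The versions differ only in the first row. There, the decision on H03B changes only if both observable p-values are at or below 0.050 and at least one is above 0.010.

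**Does the corrected step still control error?** Yes, by simple bounds over the true null hypotheses:

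- All three null: at most 0.04 + 0.005 + 0.005 = 0.05. The two versions cannot differ here, because they part only after two false rejections have already occurred. Under independence the familywise error is 1 − 0.96 × 0.995 × 0.995 = 0.0496. Simulation (4,000,000 draws, within-group gates omitted) gave 0.0497 at correlation 0 and 0.0463 at correlation 0.5, the same in both versions.
- H02B and H03B null: at most 0.045 + 0.005 = 0.05.
- H01 and H03B null: at most 0.04 + 0.010 = 0.05.
- Only H03B null, earlier hypotheses almost always rejected: 0.010 as written, 0.050 corrected.

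**Cost in power, as an illustration.** Two-sample t test, difference 50, SD 55:

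| UX007:placebo in the observable analysis | Power at 0.05 | Power at 0.01 |
|---|---|---|
| 30:10 | 0.788 | 0.530 |
| 24:8 (assumed) | 0.702 | 0.421 |
| 21:7 (assumed) | 0.649 | 0.363 |

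These powers apply once H01 and H02B have both been rejected and are not weighted by the chance of that. Under the same inputs, with assumed absence subsets of 15:5 to 24:8 and assumed correlations, that branch is reached about 44% to 60% of the time. The overall loss for H03B is then about 9 to 17 percentage points, for example 0.54 down to 0.41.

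**The case against.** The strongest reply is about weight. The fallback is one of several additional analyses, and Table 6 of the SAP lists no output for it. The primary ANCOVA does not depend on it, and observable seizures keep an unadjusted secondary test. The slip is conservative. All of this is right, and it limits the finding to this one procedure.

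A second reply is that step 1 does not settle what step 3 should carry. Since α₁ has no starred form, both steps can be read as passing on the initial allocation, and passing on less alpha is still a valid procedure. That is true as far as error control goes. But step 1 passes on the level at which its hypothesis was tested, and step 3 tests at α₂∗. Only the starred reading lets the last hypothesis reach the 0.05 allocated, as a method called fallback implies. An asterisk lost from the text cannot be fully excluded, though the others in the same step are intact. It could not explain step 5.

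A third reply is that no analyst would follow step 5 literally, because its reject arm and step 4 both name H03B. That is likely, but a prespecified decision rule should not have to be repaired by its reader.

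The criticism of the power figures is fair in part: the marginal losses of about 26 to 29 points overstate the unconditional loss, so both are given above.

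**Conclusion.** Both errors are real and should be fixed. After H01 and H02B are rejected, observable seizures are tested at 0.010 as printed and at 0.050 under the fallback method, and step 5 can contradict step 3. The 0.010 and 0.050 follow exactly from the SAP's own definitions. There is no inflation of type I error and no effect on the primary analysis. The power figures are illustrations only: they apply the overall difference of 50 and SD of 55 to observable seizures, use a t test where the plan has a log-scale ANCOVA, and assume the subset sizes.

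**What to change.** In SAP 8.6.3:

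- Step 3: set α₃∗ = α₂∗ + 0.005. This gives 0.050 if H01 and H02B are both rejected and 0.010 if only H02B is.
- Step 5: end with acceptance of H03B.
- As a clarification, add a sentence that the primary ANCOVA is judged at one-sided 0.05 and that the fallback, with H01 at 0.04, is supportive. Sections 8.1 and 8.6.3 already point that way.

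If the sponsor wants the fallback to be decisive instead, the SAP should quote primary power at 0.04, which is 0.754 for 30:10, and reconcile the procedure with the unadjusted secondary testing in Protocol 7.6.

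The cost is one asterisk, one subscript and one sentence before unblinding. Sample size, data collection and all other analyses stay as they are.
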